3.2 Study Objectives and Endpoints

| Objectives and Endpoints | |
|--|--|
| Primary Objective | Primary Endpoints |
| Safety Objective: To evaluate the safety and reactogenicity of the mRNA-1273 vaccine administered in 2 doses 28 days apart, in participants who have a | Safety Endpoints: 
Solicited local and systemic Adverse Reactions (ARs) through 7 days after each injection. |

| Objectives and Endpoints | |
|--|---|
| Primary Objective | Primary Endpoints |
| hematological malignancy and are immunosuppressed due to their disease and/or treatment, or receiving a PD-1/PDL-1 inhibitor for treatment of a solid tumor for participants who are vaccine- naïve. To evaluate the safety and reactogenicity of booster doses of mRNA-1273 vaccine administered to participants with cancer who have previously received an mRNA or alternative vaccine regimen | 
Unsolicited AEs through 28 days after each injection.SAEs throughout the entire study period.Vital sign measurements and physical examination findings. |
| Immunogenicity Objective: To assess the immunogenicity of mRNA-1273 in participants with cancer, as assessed by the titer or level of specific binding antibody (bAb) | Immunogenicity Endpoints: 
Titer or level of specific binding antibody (bAb), in participantsTiter or level of SARS-CoV-2-specific binding antibody (bAb) measured by ELISA on Day 1, Day 29, Day 36, Day 57 Day 209 and Day 394 for participants on Vaccine-Naïve CohortsTiter or level of SARS-CoV-2-specific binding antibody (bAb) measured by ELISA on Day 1, Day 29, Day 180, Day 360 for participants on Booster Vaccine Cohorts |

| Secondary Objective | Secondary Endpoints |
|---|--|
| To evaluate the immunogenicity of the mRNA-1273 vaccine administered, as assessed by the titer or level of neutralizing antibody (nAb). | For Vaccine-Naïve Cohorts: 
Titer or level of SARS-CoV-2-specific neutralizing antibody (nAb) on Day 1, Day 29, Day 36, Day 57, Day 209, and Day 394Seroconversion due to vaccination on Day 29, Day 36, Day 57, Day 209, and Day 394 measured as:
For subjects with no detectable antibody titer (< |

| Secondary Objective | Secondary Endpoints |
|---------------------|---|

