6.1.2.6 Day 394, Visit 6 (+/- 28 days)

- In-person visit
- Follow-up interim medical history and vital signs will be completed.
- Unsolicited AEs, and SAEs, that have occurred since the last contact will be collected.
- Standard antibody testing to assess immune response
- Samples will be collected for immunology/correlative studies (see section [7.3](#)).
- Participants will be thanked for participating in the study

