8.3 Type and Duration of Follow-up of Participants after Adverse Events

All AEs will be assessed for severity and relationship to study intervention. Collection of all AEs from the participant, solicited and unsolicited, will occur during the period from study product administration on Day 1 through 28 days after the last vaccination. Adverse events that are serious need to be recorded after 28 days following the last vaccine, only if they are related to the study intervention.

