8.9 Halting Rules

8.9.1 Study Halting Criteria

If any of the below occurs, the Protocol Chair will halt accrual to the trial to conduct a detailed safety review. Prior to resumption of the study, an expedited safety report will be sent to and reviewed by FDA if requested. All events also must be evaluated by the SMC.

- Any participant experiences laryngospasm, bronchospasm or anaphylaxis within 24 hours after administration of vaccine that is considered related to vaccine.
- Two (2) or more participants experience an allergic reaction such as generalized urticaria defined as occurring at three or more body parts within 72 hours after administration of vaccine that is considered related to vaccine.
- Any participant experiences suspected or confirmed myocarditis and/or pericarditis related to the study vaccine within 6 weeks of administration.
- Any serious adverse event deemed related to the vaccine will result in a halt to study accrual and an ad hoc meeting of the Safety Monitoring Committee (SMC). After a discussion of the event, the decision will be made as to whether to halt further accrual or lift the hold on accrual, based on the facts of the case and emerging evidence. Participants already on trial who successfully completed the first dose without incident will be allowed to receive the second dose of the vaccine, as per the mRNA-1273 vaccine's Emergency Use Authorization (EUA) granted in December 2020.

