19.3 Appendix C: Leukemia-specific AE Recording & Reporting Guidelines

These guidelines will be followed for the recording and reporting of adverse and serious adverse events.

- a) Baseline events will be recorded in the medical history section of the case report form and will include the terminology event name, grade, and start date of the event. Baseline events are any medical condition, symptom, or clinically significant lab abnormality present before the informed consent is signed.
 - i) Hematologic laboratory abnormalities will not be recorded as baseline
 - ii) events for participants with acute leukemia, myelodysplastic syndrome,
 - iii) chronic lymphocytic leukemia, or chronic myeloid leukemia in blast phase.
 - iv) If exact start date is unknown, month and year or year may be used as the start date of the baseline event.
- b) The maximum grade of the adverse event will be captured per course or protocol defined visit date.
- c) These adverse events will be recorded in the case report form:
 - i) Any grade adverse event that is possibly, probably, or definitely related to the study drug(s).
 - ii) All serious adverse events regardless of attribution to the study drug(s).
 - iii) Any grade adverse event regardless of attribution to the study drug(s) that results in any dose modification.
- d) Hematologic adverse events will not be recorded or reported for studies in participants with acute leukemia, myelodysplastic syndrome, chronic lymphocytic leukemia, or chronic myeloid leukemia in blast phase except for:
 - i) Prolonged myelosuppression as defined by the NCI-CTCAE criteria specific for leukemia, e.g., marrow hypocellularity on day 42 or later (6 weeks) from start of therapy without evidence of leukemia (< 5% blasts), or that results in dose modifications, interruptions or meets the protocol definition of DLT or SAE.
- e) Serious adverse events will be reported according to institutional policy.
- f) Protocol specific language regarding the recording and reporting of adverse and serious adverse events will be followed in the event of discordance between the protocol and Leukemia-specific adverse event recording and reporting guidelines.

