19.6 Appendix F: Study Calendar: Vaccine Naïve Arms

| Procedures | Screening ^e | | Baseline ^e (-28 days)/ Day 1 | | D29 (+3 days) ^e | | D36 (+/- 1 day) ^e | | D57 (+/- 7 day) ^e | | D209 (+/- 28 day) ^e | | Final Study Visit (+/- 28 days) ^e | | Unscheduled Visit | Early Termination Visit | | | |
|---|------------------------|--------------|---|---|----------------------------|----|------------------------------|-----|------------------------------|---|--------------------------------|---|---|---|-------------------|-------------------------|--|--|--|
| | Day Number | Visit Number | 0 | 1 | 29 | 36 | 57 | 209 | 394 | 0 | 1 | 2 | 3 | 4 | 5 | 6 | | | |
| Informed Consent | X | | | | | | | | | | | | | | | | | | |
| Review Eligibility Criteria | X | X | | | | | | | | | | | | | | | | | |
| Medical History | X | | | | | | | | | | | | | | | | | | |
| Concomitant Medications | X | | | | | X | | | | | | | | | | | | | |
| Vaccination ^d | | | X | | X | | | | | | | | | | | | | | |
| Telephone Contact | | | | | | | | | | | | | | | | | | | |
| Physical Examination ^a | X | X | | | X | | | | | | | | | | | | | | |
| Vital Signs | X | X | | | X | | X | | | | | | | | | | | | |
| Height and Weight (for Body Mass Index [BMI]) | X | | | | | | | | | | | | | | | | | | |
| Electrocardiogram (ECG) | | X | | | X ^g | | X ^g | | | | | | | | | | | | |
| Labs (see section 6.1) ^b | X | X | | | X | | X | | | | | | | | | | | | |
| Pregnancy Test ^c | X | X | | | X | | | | | | | | | | | | | | |
| Memory aids: Solicited AEs | | | Days 1-8 | | Days 29-36 | | | | | | | | | | | | | | |
| Unsolicited AEs and SAEs ^f | | | Days 1- 28 days after final vaccination | | | | | | | | | | | | | | | | |
| Correlative Studies | | | Please see section 7.3 | | | | | | | | | | | | | | | | |

Study Calendar Key:

- a) Full physical examination will be performed at screening and physical examination. The participants will be asked to provide all information surrounding a COVID19 infection, should this occur.
- b) Hematology and Chemistry: Clinical screening laboratory evaluations will include tests as mentioned in the table.
- c) For women of childbearing potential serum/urine pregnancy test at screening, and on Days 1 (within one week) and 29 with results confirmed as negative prior to administration of each vaccination. Results of the pregnancy test will not be required prior to verifying the order.

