19.7 Appendix G: Study Calendar Booster Vaccine Arms ^g

| Procedures | Screening ^e | Baseline ^e (-28 days)/ Day 1 | | D8 (+/- 1 day). Mandatory for CAR-T Cell Cohort only | | D29 (+/- 3 day) ^e | D57 (+/- 7 day) ^e | D180 (+/- 28 day) ^e | Final Study Visit- (+/- 28 days) ^e | Unscheduled Visit | Early Termination Visit |
|---|------------------------|---|---|---|-------------------|------------------------------|------------------------------|--------------------------------|--|-------------------|-------------------------|
| | Day Number | 0 | 1 | 8 | 29 | 57 | 180 | 360 | | | |
| | Visit Number | 0 | 1 | 2 | 3 | 4 | 5 | 6 | | | |
| Informed Consent | X | | | | | | | | | | |
| Review Eligibility Criteria | X | X | | | | | | | | | |
| Medical History | X | | | | | | | | | | |
| Concomitant Medications | X | | | | | | | | | | |
| Vaccination ^d | | X | | | | | | | | | |
| Telephone Contact | | | | | | | | | | | |
| Physical Examination ^a | X | X | | | | | | | | | |
| Vital Signs | X | X | | | | | | | | | |
| Height and Weight (for Body Mass Index [BMI]) | X | | | | | | | | | | |
| Electrocardiogram (ECG) | | X | | | X ⁱ | | | | | | |
| Labs (see section 6.1) ^b | X | X | X | X | X ^{f103} | | | | | | |
| Pregnancy Test ^c | X | X | | | | | | | | | |
| Memory aids: Solicited AEs | | Days 1-8 | | | | | | | | | |
| Unsolicited AEs and SAEs ^h | | | | Days 1-28 days after final vaccination | | | | | | | |
| Correlative Studies | | | | Please see section 7.3 | | | | | | | |

Study Calendar Key:

- a) Full physical examination will be performed at screening and physical examination. The participants will be asked to provide all information surrounding a COVID19 infection, should this occur. Physical examination will be optional for participants transitioning from Vaccine-Naïve Cohorts.
- b) Hematology and Chemistry: Clinical screening laboratory evaluations will include tests as mentioned in the table. Participants with CLL will also have LDH and Beta-2 microglobulin drawn on Days 1, 29 and 57. Results from laboratory evaluations will not be required prior to administering the vaccine on participants transitioning from Vaccine-Naïve Cohorts.
- c) For women of childbearing potential serum/urine pregnancy test within one week of vaccination with results confirmed as negative prior to administration the vaccination. Results of the pregnancy test will not be required prior to verifying the order.

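### The primary SAE endpoint covers the whole study, but section 8.3 and both calendars record late SAEs only if related, while the late-visit text asks for all of them

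*Combined protocol and SAP*

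**What the plan says.** **Endpoint and analysis.** The primary safety endpoints in section 3.2 include "SAEs throughout the entire study period". No restriction to related events is given. Section 11.4.2.2 lists SAEs and treatment-related SAEs as separate items to be summarised, so the endpoint cannot be read as meaning related SAEs only.

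**Collection rule.** Section 8.3 says that collection of all AEs "will occur during the period from study product administration on Day 1 through 28 days after the last vaccination". It then says: "Adverse events that are serious need to be recorded after 28 days following the last vaccine, only if they are related to the study intervention". Note f to the vaccine-naïve calendar (Appendix F) and note h to the booster calendar (Appendix G) repeat both sentences. The calendar rows for unsolicited AEs and SAEs read "Days 1- 28 days after final vaccination" (naïve) and "Days 1-28 days after final vaccination" (booster).

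**Visit text.** The procedures for Days 209 and 394 (naïve) and Days 57, 180 and 360 (booster) each say: "Unsolicited AEs, and SAEs, that have occurred since the last contact will be collected". Section 6.1.4 adds a six-month call to collect new SAEs from those who withdraw within 7 days of their last dose. Section 8.5 requires 24-hour submission of AEs that meet the serious criteria. None of these carries a causality limit.

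**The concern.** A primary endpoint should be something the collection rules can deliver. Here the endpoint and the visit lists say all SAEs to the end of the study, while the safety section and both calendars say related SAEs only once 28 days have passed since the last dose. A site could follow either set of instructions and believe it was compliant.

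The trial tests no hypothesis (section 11.1), so the descriptive SAE percentages are themselves the primary safety result. If ascertainment changes part-way through follow-up, the line for all SAEs becomes a mixture: every SAE early on, then either every SAE or only those an investigator judged related, depending on which text the site followed. Some late signals are also poorly served by case-by-case causality. Section 2.5.1 names vaccine-associated disease enhancement as a theoretical risk. A late serious COVID-19 admission could reasonably be called unrelated in the individual, although an excess would show only in aggregate. Events that were never recorded may not be reliably recoverable at analysis.

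**Working it through.** **Step 1. Set the passages side by side.**

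| Place | SAEs later than 28 days after the last dose |
|---|---|
| 3.2, primary endpoint | All, entire study |
| 11.4.2.2, analysis | All, with related SAEs as a separate item |
| 8.3; notes F(f) and G(h) | Related only |
| Calendar rows, Appendices F and G | Collection ends at 28 days (the notes add back related SAEs) |
| 6.1.2.5, 6.1.2.6 (naïve); 6.1.3.4 to 6.1.3.6 (booster) | All since the previous contact |
| 6.1.4, early-termination call | Any new SAE |
| 8.5, expedited reporting | Any event meeting the serious criteria |

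Section 8.4 calls for documentation regardless of relationship, but only within the collection and reporting period. It therefore does not settle what happens after 28 days.

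**Step 2. Day counts.** The plan gives no figure of its own to reproduce. The inputs are the dosing days (29 for the second naïve dose, 1 for the booster), the last study days (394 and 360, section 3.1) and the 28-day limit (section 8.3).

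- End of full collection = last dose day + 28.
- Related-only period = last study day − end of full collection.
- Follow-up from Day 1 = last study day − 1.

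Vaccine-naïve: 29 + 28 = Day 57; 394 − 57 = 337 days; 394 − 1 = 393 days; 337/393 = 85.8%, about 86%.

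Booster, one dose: 1 + 28 = Day 29; 360 − 29 = 331 days; 360 − 1 = 359 days; 331/359 = 92.2%, about 92%.

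Under the first fix below, the related-only period is 0 days in both groups, which matches section 3.2.

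**Step 3. Dependence on later boosters.** The window is tied to the last vaccination, and up to three booster doses are allowed on study. Each one extends full collection. Read literally, whether an unrelated SAE on, say, Day 100 falls inside the window can depend on whether that participant later takes another dose.

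**Step 4. Illustration in events (assumption, not in the documents).** Suppose a constant hazard of first unrelated SAE, with risk R by the last visit. The proportion of participants with such an event inside the full-collection window is 1 − (1 − R)^(W/T). Here W/T is 56/393 for naïve and 28/359 for booster.

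| R to last visit | Naïve, inside window | Booster, inside window |
|---|---|---|
| 10% | 1.5% | 0.8% |
| 30% | 5.0% | 2.7% |
| 50% | 9.4% | 5.3% |

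If section 8.3 were followed strictly, the recorded percentage with an unrelated SAE would be a small fraction of the true one across this range.

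**The case against.** Limiting late collection to related SAEs is a legitimate choice in a year-long study of cancer patients, whose hospital admissions will often have other causes. Related SAEs are kept throughout, there is no control arm, and the analysis is descriptive. All of that stands, but it is an argument for restating the endpoint, not for leaving the two texts in conflict.

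Four stronger readings are tempting, and the documents do not support them.

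- **That unrelated late SAEs will go unrecorded.** The late-visit lists, the early-termination call and section 8.5 all ask for them. The documents show conflicting instructions, not a settled omission.
- **That Appendix C adds a further contradiction.** It does ask for all SAEs regardless of attribution. However, it is leukaemia-specific, and its item f gives way to protocol-specific language where the two disagree.
- **That the SAE results are not comparable between cohorts.** The same rule applies to every cohort, and no between-cohort bias is shown. Inconsistent recording is possible because sites may follow different text, and that is as far as it goes.
- **That the halting rule for "myocarditis and/or pericarditis related to the study vaccine within 6 weeks of administration" has a blind spot between 28 days and 6 weeks.** Section 8.1.5 makes these events AESIs, reported on the SAE form to SAE timelines, with no 28-day limit stated. Section 8.5 gives the 24-hour timeline, and Appendix E provides for referral and follow-up. Any gap in routine AE collection arises only after the last dose: six weeks after the first naïve dose ends at about Day 43, inside the window that runs to Day 57. A clarifying cross-reference is the most that is needed.

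**Conclusion.** The point holds as an internal contradiction about a primary endpoint. As written, the rule in section 8.3 and the two calendars cannot deliver the SAE endpoint in section 3.2 or the all-SAE summary in section 11.4.2.2, and the visit text contradicts that rule. Unrelated late SAEs may be recorded inconsistently or not at all.

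The conflict covers about 86% of scheduled follow-up in the vaccine-naïve cohorts and about 92% in the booster cohorts. These figures assume on-schedule dosing and no later on-study booster, and they ignore visit windows. They describe time rather than events. The number of SAEs affected cannot be derived from the documents, and the event figures above rest on an assumed hazard. It should be corrected because it changes what the primary SAE percentages mean.

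**What to change.** Choose one rule and state it everywhere.

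**Preferred.** In section 8.3, the unsolicited AE/SAE rows of both calendars, and notes F(f) and G(h), say that all SAEs are recorded from first dose through the final visit regardless of relationship, and that non-serious unsolicited AEs are recorded to 28 days after each dose. Sections 3.2 and 11.4.2.2 can then stay as they are. In the late-visit lists, limit the non-serious part of the sentence to match. The cost is protocol wording, the eCRF completion guideline and a modest number of extra SAE forms. The visits already take place and already ask about SAEs.

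**Alternative.** Keep section 8.3 and restate the primary endpoint and the 11.4.2.2 summary as all SAEs to 28 days after the last dose and related SAEs thereafter. Then align the late-visit text, the early-termination call and section 8.5. This costs wording only, but gives up the all-SAE result for most of follow-up. It should also say how the window is defined for participants who take further boosters.

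Under either option, one sentence in section 8.3 could state that AESIs under section 8.1.5 are reported irrespective of the 28-day limit.

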8.4 Assessment of Safety Events

AE information collected will include event description, date of onset, assessment of severity and relationship to study product and alternate etiology (if not related to study product), date of resolution of the event, seriousness and outcome. The assessment of severity and relationship to

the study product will be done only by those with the training and authority to make a diagnosis and listed on the Form FDA 1572 as the site principal investigator or sub-investigator. AEs occurring during the collection and reporting period will be documented appropriately regardless of relationship. AEs will be followed through resolution.

SAEs will be:

- Assessed for severity and relationship to study product and alternate etiology (if not related to study product) by a licensed study physician listed on the Form FDA 1572 as the site principal investigator or sub-investigator.
- Recorded on the appropriate SAE report form, the medical record and captured in the clinical database.
- Followed through resolution by a licensed study physician listed on the Form FDA 1572 as the site principal investigator or sub-investigator.

An abnormal laboratory value which cannot be attributed to chemotherapy for malignancy will be recorded in the database as an AE **only** if the laboratory abnormality is characterized by any of the following:

- Results in discontinuation from the study
- Is associated with clinical signs or symptoms
- Requires treatment or any other therapeutic intervention
- Is associated with death or another serious adverse event, including hospitalization.
- Is judged by the Investigator to be of significant clinical impact
- If any abnormal laboratory result is considered clinically significant, the investigator will provide details about the action taken with respect to the study intervention and about the participant's outcome.

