8.5 Reporting of Serious Adverse Events

Any AE that meets protocol-defined serious criteria or meets the definition of Adverse Event of Special Interest that require expedited reporting must be submitted immediately (within 24 hours of awareness) to OSRO Safety using the CCR SAE report form.

All SAE reporting must include the elements described in section [8.4](#)

SAE reports will be submitted to the Center for Cancer Research (CCR) at: [contact] and to the CCR PI and study coordinator. CCR SAE report form and instructions can be found at: <https://ccrod.cancer.gov/confluence/pages/viewpage.action?pageId=157942842>

Following the assessment of the SAE by OSRO, other supporting documentation of the event may be requested by the OSRO Safety and should be provided as soon as possible.

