8.8 Regulatory Reporting for Studies Conducted Under CCR-Sponsored IND

Following notification from the investigator, CCR, the IND sponsor, will report any suspected adverse reaction that is both serious and unexpected. CCR will report an AE as a suspected adverse reaction only if there is evidence to suggest a causal relationship between the study product and the adverse event. CCR will notify FDA and all participating investigators (i.e., all investigators to whom the sponsor is providing drug under its INDs or under any investigator's IND) in an IND safety report of potential serious risks from clinical trials or any other source, as soon as possible, in accordance to 21 CFR Part 312.32.

All serious events will be reported to the FDA at least annually in a summary format.

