11.4.2.2 Safety Analyses

Safety and reactogenicity will be assessed by clinical review of all relevant parameters including solicited ARs (local and systemic events), unsolicited AEs, SAEs, AEs leading to discontinuation, safety laboratory test results, vital signs, and physical examination findings.

Solicited ARs and unsolicited AEs will be coded by system organ class (SOC) and preferred term according to the MedDRA for adverse reaction terminology. The Toxicity Grading Scale for Healthy Adult and Adolescent Volunteers Enrolled in Preventative Vaccine Clinical Trials (DHHS 2007) is used in this study with modification for rash, solicited ARs, unsolicited AEs, and vital signs.

Rash will be graded as:

- Grade 0 = no rash
- Grade 1 = localized without associated symptoms
- Grade 2 = maculopapular rash covering $< 50\%$ body surface area
- Grade 3 = urticarial rash covering $> 50\%$ body surface area
- Grade 4 = generalized exfoliative, ulcerative or bullous dermatitis

All safety analyses will be based on the Safety Set, except summaries of solicited ARs which will be based on the Solicited Safety Set. All safety analyses will be provided overall and by cohort.

The number and percentage of participants with any solicited local AR, with any solicited systemic AR and with any solicited AR during the 7-day follow-up period after each injection will be provided with a 2-sided 95% exact CI using the Clopper-Pearson method.

Number and percentage of participants with unsolicited AEs, SAEs, Grade 3 or higher ARs and AEs, treatment-related AEs and SAEs, and AEs leading to discontinuation from study vaccine or participation in the study will be summarized. Unsolicited AEs will be summarized by system organ class and/or preferred term coded by MedDRA.

For treatment-emergent safety laboratory tests results, the raw values and change from baseline values will be summarized by timepoint.

The number and percentage of participants who have chemistry, hematology, coagulation, and vital signs results below or above the laboratory normal ranges will be tabulated by timepoint.

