- d) Participants in the vaccine naïve cohort will receive an injection of mRNA-1273 into muscle on Days 1 and 29 and will be followed through 12 months post second vaccination (Day 394). Participants will receive proof of vaccination on Day 29 after administration of their second dose of study drug.
- e) In-person clinical visits will occur at screening, and on Baseline/Days 1 (may occur on same day), 29, 36, 57, 209 and at 394. These visits at clinic will take approximately 4-6 hours.
- f) Collection of all AEs from the participant, solicited and unsolicited, will occur during the period from study product administration on Day 1 through 28 days after the last vaccination. Adverse events that are serious need to be recorded after 28 days following the last vaccine, only if they are related to the study intervention.
- g) The ECG may be performed up to 2 weeks prior to Day 29. The ECG may be performed up to 2 weeks before or 2 weeks after Day 57.

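### The protocol's collection rules stop recording unrelated SAEs 28 days after the last dose, while the primary safety endpoint counts SAEs over the whole study

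*Combined protocol and SAP*

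**What the plan says.** **The restrictive text.** Section 8.3 collects all AEs from Day 1 until 28 days after the last vaccination. Beyond that, SAEs "need to be recorded after 28 days following the last vaccine, only if they are related to the study intervention". Footnote f of the vaccine-naïve calendar (Appendix F) and footnote h of the booster calendar (Appendix G) carry the same sentence, ending "only if they are related to the study intervention". In both calendars, the row to which the footnote is attached covers unsolicited AEs and SAEs together and ends 28 days after the final vaccination, with no separate span for SAEs.

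**The endpoint.** Section 3.2 lists among the primary safety endpoints "SAEs throughout the entire study period", with no condition on relatedness. The neighbouring entry limits unsolicited AEs to 28 days after each injection, so the longer SAE window looks deliberate.

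**The analysis.** Section 11.4.2.2 plans "Number and percentage of participants with unsolicited AEs, SAEs, Grade 3 or higher ARs and AEs, treatment-related AEs and SAEs". It sets no time window for SAEs and does not say whether they are all-cause.

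**Other text on relatedness.** Section 8.1.1.2 says that relatedness does not decide what is reported in the trial. The opening of section 8.1 leans the other way: it bases the safety assessment on treatment-related adverse events.

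**The concern.** A primary endpoint can be no more complete than the rule that collects its data. Here the endpoint covers all SAEs to the end of study, and the section on duration of follow-up tells sites to drop the unrelated ones after 28 days. Sites work from the calendars, and the calendars repeat the restriction.

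Two consequences are possible. First, the SAE row of the safety summary would mix all-cause events up to 28 days after the last dose with related-only events afterwards, under one label. Second, the two sites could follow different rules, and nothing in the data would show it.

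All participants are vaccinated and the study is open-label, so there is no unvaccinated group against which to check an investigator's call on relatedness. Section 2.5.1 names a theoretical risk of disease enhancement and says it is unknown whether the vaccine increases it. A COVID-19 hospitalisation months after the last dose, judged unrelated, is the kind of event a later reader would want to see, and under section 8.3 it need not be recorded as an SAE.

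**Working it through.** The plan gives no figure to reproduce. The check has two parts: whether any text settles the conflict, and how much follow-up the restriction covers.

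**1. Does other text settle it?**

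- *Late visits (6.1.2.5, 6.1.2.6, 6.1.3.5, 6.1.3.6).* They collect SAEs since the last contact with no relatedness condition. The same line also asks for unsolicited AEs, whose endpoint stops at 28 days, so it may be repeated visit wording.
- *Section 6.1.4.* It requires a six-month call for new SAEs, but only for participants who withdraw within 7 days of a dose.
- *Section 8.4.* SAEs are to be "Recorded on the appropriate SAE report form, the medical record and captured in the clinical database". Its instruction to document events whatever their relationship applies only within the collection and reporting period, which is the period in dispute.
- *Section 8.5.* It requires submission within 24 hours of "Any AE that meets protocol-defined serious criteria". It sets no explicit time limit, but it governs how to report, and its clause on expedited reporting can be read as a qualifier.
- *Section 8.8.* "All serious events will be reported to the FDA at least annually in a summary format" describes what the sponsor sends to the FDA, not what sites collect.
- *Appendix C.* It records all SAEs whatever their attribution, but it is leukemia-specific and yields to protocol-specific language, which could mean section 8.3.

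Most of this points towards full capture. None of it overrides section 8.3.

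**2. How much follow-up is affected if section 8.3 governs?**

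Inputs: last dose on Day 29 and follow-up to Day 394 for naïve participants; dose on Day 1 and follow-up to Day 360 for boosters (section 3.1); full AE collection to 28 days after the last dose (section 8.3); final visit window of ±28 days and minimum booster spacing of 28 days (section 6.1.3 and the calendars).

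Restricted share = (final day − (last dose day + 28)) / (final day − 1)

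| Schedule | Nominal | Final visit 28 days early | Final visit 28 days late |
|---|---|---|---|
| Naïve, two doses | (394 − 57)/(394 − 1) = 337/393 = 85.8% | 309/365 = 84.7% | 365/421 = 86.7% |
| Single booster | (360 − 29)/(360 − 1) = 331/359 = 92.2% | 303/331 = 91.5% | 359/387 = 92.8% |
| Three boosters, 28 days apart | 331/(359 + 56) = 331/415 = 79.8% | 303/387 = 78.3% | 359/443 = 81.0% |
| Naïve plus three boosters (Days 1, 29, 57, 85, 113) | 331/(359 + 112) = 331/471 = 70.3% | 303/443 = 68.4% | 359/499 = 71.9% |

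Each further booster resets the calendar. At minimum spacing the 28-day windows join, which lowers the share.

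If section 3.2 governs, the restricted share is zero in every row. With all SAEs recorded to the final visit, full capture would run for 393 days instead of 56 (naïve) and 359 instead of 28 (single booster). No sample size or precision statement in section 11 depends on this.

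**The case against.** The best defence is that section 8.3 is the governing text. It is the section on duration of follow-up, both calendars repeat its rule, and section 8.1 opens by framing safety around treatment-related events. Related-only capture of late SAEs can be a legitimate design; on that view only the endpoint line in section 3.2 is loosely worded. What stands is that this is a possible intention. But section 8.1.1.2 states the opposite principle within the same chapter, and no clause ranks the texts. Even on this view, the primary endpoint needs editing.

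A reader might infer that section 11.4.2.2 contradicts section 8.3 outright. The text does not go that far. Both all-cause and related SAEs exist up to 28 days after the last dose, so the two can be listed separately under either rule. The summary is affected only by implication, through a change of definition part-way along follow-up.

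The defence can also say that some late events would surface elsewhere: the calendars ask for information on any COVID-19 infection, post-infection blood draws are offered as optional, and death is an off-study reason. That is fair, but none of these routes fills the SAE table.

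Finally, the study tests no hypothesis, the event-specific halting rules and the general SAE halting rule in section 8.9.1 turn on vaccine-related events, and related SAEs are kept throughout. All of this stands and limits the consequence.

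**Conclusion.** The inconsistency is real: section 8.3, both footnotes and both calendar rows cannot be followed while also capturing the primary safety endpoint as section 3.2 defines it. It should be corrected. It is a mismatch between collection rule and endpoint; the planned analysis methods are not at fault.

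The size depends on which text sites follow: 86% of nominal follow-up time for naïve participants and 92% after one booster if section 8.3 governs, about 70% to 80% with three boosters at minimum spacing, and zero if section 3.2 governs. These figures assume nominal visit days, with the window ranges tabulated above.

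A reader might take 86% and 92% as shares of SAEs lost, or take the loss as certain. Neither follows. They are shares of calendar time, the documents give no SAE rate or relatedness split from which to count events, and sites may in practice collect everything. Nor are the halting rules weakened, since they rest on related events.

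**What to change.** In section 8.3, footnote f of Appendix F, footnote h of Appendix G and the AE/SAE row of each calendar, state one rule: all SAEs are recorded from Day 1 through the final study visit (Day 394 for naïve participants, Day 360 after the last booster for anyone boosted) regardless of relatedness, and non-serious unsolicited AEs end 28 days after the last vaccination. The calendar rows must change too; otherwise the corrected footnotes would contradict the rows they annotate. Splitting each row into a non-serious line and an SAE line does this.

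No visits are added, because the late visits already ask about SAEs. The cost is more SAE reports, possibly many. The cohorts include intensive leukemia chemotherapy, CAR T-cell therapy and allogeneic transplant (section 4.6), and section 7.2.2.2 describes infection from myelosuppression as common. If that load is a concern, late unrelated SAEs can be recorded in the database while the 24-hour submission is kept for related ones. That is optional and needs a matching edit to section 8.5.

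If related-only late capture was intended, narrow the endpoint in section 3.2 to all SAEs through 28 days after the last dose and related SAEs thereafter, and label the SAE summary in section 11.4.2.2 the same way.
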